### 5.3 Duration of the study and the follow up period

Accrual time: 24 months	Treatment: 18 months	Follow-up: 18 months
-------------------------	----------------------	----------------------

Assuming an accrual time of 24 months and duration of treatment (of the last included patient) of approximately 18 months the duration of the study will be approximately 42 months. The duration of the follow up period will be 18 months.

#### ***End of study***

The study will end one month after the end of therapy of last patient.

### 5.4 Central bone marrow diagnostics and shipment modalities

The diagnosis of AML will be performed at the participating centers. In order to assure highest quality standards a central review of the cytomorphological diagnosis will be performed. Molecular genetic analyses that are either required for risk stratification (Flt3-ITD and Flt3 point mutations, NPM1 mutations, AML1-ETO, inv(16), or necessary to exclude leukemia entities not covered by the protocol (Bcr-Abl, PML-RARalpha) will be done in a centralized way. Additionally, karyotype analyses should be done centrally. In any case, karyotype analyses must be both shared for central review and for risk stratification purpose by the Studienzentrale latest at day 7 after treatment start.

#### 5.4.1 Requested material and shipment modalities

Immediately at diagnosis, please collect for central diagnostics
15 ml heparinized bone marrow
5 ml bone marrow aspirate in EDTA
20 ml heparinized peripheral blood (if blasts are present)
at least 10 unstained bone marrow smears
2 unstained peripheral blood smears

*Table 16: Bone marrow diagnostics: requested material*

Shipment is recommended from Monday through Friday and will be organized by the Studienzentrale SAL after the center has faxed the patient registration form (Patientenmeldebogen) to [name]. Material will be picked up until the afternoon from Monday to Friday and be delivered by overnight express to the following addresses:

Universitätsklinikum Carl Gustav Carus

Med. Klinik und Poliklinik I

Hämatologisches Labor Haus 65 a

[name]

[name]

[contact]

[contact]

For information on results, please contact:

[name]. [name]

[contact]

*Table 17: Material shipment address*

#### **5.4.2 Molecular genetic analyses**

For the central cell repository and the central molecular genetic analyses bone marrow aspirate and peripheral blood of each patient has to be sent to Dresden at diagnosis.

For further investigations the remaining material will be cryo-preserved at the central study office. Upon consultation with the study group it will be at the disposal of interested working groups for scientific investigations.

#### **5.4.3 Cytomorphologic examination and cytochemistry**

Initial leukemia diagnostics and differentiation are based on the morphology of peripheral blood and bone marrow smears as well as on cytochemical examinations. If the bone marrow aspirate is not available, diagnosis will be based on the bone marrow biopsy.

A Pappenheim staining, a peroxidase reaction and an esterase reaction are performed. Diagnosis and classification of the AML will be performed according to FAB criteria as well as according to the WHO classification. These analyses will be performed in the local participating centers. The central study offices participate in round robin tests within the scope of the network of excellence for acute and chronic leukemias and offer reference laboratory diagnostics for discussion of questionable cases. To be able to quickly assess the diagnostic material, bone

marrow and peripheral blood smears are requested for all patients at diagnosis (for shipping modalities, see above). Discrepancies between diagnostic results between the local participating center and the central cytomorphology will be resolved by discussion. For discussion of cytomorphology, one of the persons below can be contacted.

PD Dr. [name], Dr. [name]

Medizinische Klinik und Poliklinik I

Universitätsklinikum Carl Gustav Carus an der

Technischen Universität Dresden

Hämatologisches Labor Haus 65a

[name]

[name]

[contact]

[contact]

#### **5.4.4 Immunophenotyping**

An immunologic typing of the leukemia cells will be performed for all patients. These analyses are performed centrally. The immunophenotyping should contain the antigen CD56 and should be performed according to the proposals by the network of excellence "Acute and chronic leukemias". For discussion of flow cytometry data can be contacted:

Dr. [name]

Medizinische Klinik und Poliklinik I

Universitätsklinikum Carl Gustav Carus an der

Technischen Universität Dresden

Hämatologisches Labor Haus 65a

[name]

[name]

[contact] [name]

[contact]

For shipment modalities and required material see chapter 5.4.

### 5.4.5 Cytogenetics

For each patient a cytogenetic examination has to be immediately performed at diagnosis. Chromosomal G-Banding will be performed. Molecular genetic analyses and fluorescent-in-situ-hybridizations will be performed if necessary. There is a centralized cytogenetic analysis conducted in the SAL study center Dresden. If in exceptional cases centers are not able to participate in the centralized cytogenetic analysis, the center that work together with local cytogenetic laboratory have to ensure that karyotype analysis will be completed at day 7 in order to provide the requested information for stratification of the patients. Cytogenetic laboratories should fax the study center and the "Studienzentrale" the results of the analysis as soon as the analysis is completed. For discussion of cytogenetic data can be contacted:

Dr. [name]

Medizinische Klinik und Poliklinik I

Universitätsklinikum Carl Gustav Carus an der

Technischen Universität Dresden

Hämatologisches Labor Haus 65a

[name]

[name]

[contact] [name]

[contact]

## 6 ASSESSMENT OF SAFETY

### 6.1 Adverse Event definitions

Adverse Events and Serious Adverse Events will be graded according to the National Cancer Institute Common Toxicity Criteria (CTC) 3.0 for Cancer Clinical Trials.

#### ***Definition of Adverse Event (AE)***

An Adverse Event (AE) is any untoward medical occurrence in a clinical investigation patient administered a pharmaceutical product and which does not necessarily have a causal relationship with this treatment. An adverse event (AE) can therefore be any unfavorable and unintended sign, symptom, disease or exacerbation of a preexisting condition temporally associated with the use of a medicinal (investigational) product, whether or not related to the medicinal product.

Symptoms of the disease under study should not be classified as AEs as long as they are within the normal day-to-day fluctuation or expected progression of the disease.

The reporting of abnormal laboratory values should be avoided unless they lead to clinical consequences that are not routine.

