### **2.3.2 Secondary**

- to compare the median EFS of AML patients with Flt3-ITD mutations between the Sorafenib and the control group
- to compare the median EFS of the patients in each of the six strata:
  1. HR cytogenetics: yes
  2. LR cytogenetics: yes
  3. HR and LR cytogenetics: no and NPM1-Mut: yes, Flt3 Mut: yes
  4. HR and LR cytog.: no and NPM1-Mut.: yes, Flt3 Mut.: no
  5. HR and LR cytog.: no and NPM1-Mut.: no, Flt3 Mut.: yes
  6. HR and LR cytog.: no and NPM1-Mut.: no, Flt3-Mut.: no
- to compare the median Overall Survival (OS) of AML patients with Flt3-ITD mutations between the Sorafenib and the control group
- to compare the median Overall Survival (OS) of all AML patients between the Sorafenib and the control group
- to compare the CR rate of the Sorafenib with the control group
- to compare the rate of molecular remissions of the Sorafenib with the control group
- to compare the toxicity of the Sorafenib and the control treatment
- to compare the evidence of minimal residual disease of all AML patients between the Sorafenib and the control group after induction therapy and in the course of the first remission
- to compare early treatment efficacy (day 16 bone marrow assessment) between the Sorafenib and the control group
- to compare the development of biomarkers indicating the course of disease, including genetic, epigenetic, transcriptional and protein markers in leukemic blasts, bone marrow, peripheral blood cells, serum and plasma

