*Patients who develop grade 3 fever/ chills, grade 3 elevation of hepatic transaminases with ALT and AST <10x ULN, grade 3 hyperlipasemia or hyperamylasemia without clinical or other evidence of pancreatitis may continue Sorafenib/ Placebo treatment without interruption at the discretion of the investigator. Also excludes nausea/ vomiting that has not been premedicated, and diarrhea. If no recovery after 30 day delay, treatment will be discontinued unless patient is deriving clinical benefit. If more than 2 dose reductions are required, treatment will be discontinued.				

*Table 4: Dose modifications for Sorafenib-associated non hematological toxicity except hand-foot skin reactions and hypertension*

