## **Evaluations during treatment**

(for full details about timepoints of evaluations please refer to the “schedule of evaluations”)

- Bone marrow aspirate (and biopsy)
- Asservation of vital bone marrow cells (Ficoll-treated bone marrow), bone marrow RNA, DNA and protein lysates, serum and plasma in a central tissue repository
- Control of CBC (with differential and platelets), coagulation and serum chemistries (including amylase, lipase and phosphate)
- Performance status
- Physical examination
- Body weight
- Diagnostic procedures i.e. in case of severe infections will follow standard procedures and should include diagnostic measures such as chest x-ray, ultrasound, urinalysis
- Evaluations performed before the first course of induction therapy will be repeated prior to each following course if necessary in the investigator’s opinion
- ECG and echocardiography as often as necessary in the investigator’s opinion
- Daily measurement of blood pressure during the first three weeks of Sorafenib/ Placebo treatment and weekly for the following three weeks Sorafenib/ Placebo treatment

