## 5.2 Schedule of evaluations

	Within 10 days prior to the first course of induction therapy	Between day 1 and day 22 of first course of induction chemotherapy	Early response evaluation (d 16)	Before the second course of induction therapy	From day 1 of second course of induction chemotherapy until start of consolidation therapy	Remission control – latest 35 days after the beginning of second induction	Before each course of consolidation therapy	From the beginning of first course of consolidation until the end of third course of consolidation = beginning of maintenance therapy	Postremission control latest day 35 after begin of each course of consolidation therapy
Informed consent	X								
Medical history	X								
Performance status and physical examination	X			X			X		
Vital Signs (blood pressure and pulse) a	X	Daily measurement of blood pressure		X	weekly		X	weekly	
Body weight and height	X			X			X		
CBC (with differential and platelets) a	X	3 times / week		X	weekly	X	X	weekly	X
Chemistry and coagulation a	X	3 times / week		X	weekly		X	weekly	

	Within 10 days prior to the first course of induction therapy	Between day 1 and day 22 of first course of induction chemotherapy	Early response evaluation (d 16)	Before the second course of induction therapy	From day 1 of second course of induction chemotherapy until start of consolidation therapy	Remission control – latest 35 days after the beginning of second induction	Before each course of consolidation therapy	From the beginning of first course of consolidation until the end of third course of consolidation = beginning of maintenance therapy	Postremission control latest day 35 after begin of each course of consolidation therapy
ECG and echocardiography a	X			X			X		
Pregnancy test e	X								
Bone marrow aspirate	X		X			X			X b
Bone marrow biopsy	X								
Bone marrow and blood samples for exploratory research	X		X			X			X b

Table 14: Schedule of evaluation I (prior to and during induction/ consolidation therapy)

	Start of maintenance therapy	During maintenance therapy	End of maintenance therapy	Follow-up 3, 6, 9, 12, 15 and 18 months after end of maintenance therapy	Relapse (during study treatment or follow-up)
Performance status and physical examination	X	monthly	X	X	
Vital Signs (blood pressure and pulse) a	X	monthly	X		

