## **6.2 Safety monitoring and reporting of AEs**

AEs and SAEs will be recorded from the time the informed consent is signed, up to and including 30 days following last administration of study drug.

Severity of adverse events and serious adverse events will be graded according to the National Cancer Institute Common Terminology Criteria for Adverse Events (CTCAE) 3.0 for Cancer Clinical Trials.

All adverse events have to be recorded on the appropriate adverse event pages in the CRF.

The National Coordinating Investigator (LKP) is responsible for central safety monitoring and reporting on behalf of the sponsor and has installed a central safety desk located at the Studienzentrale SAL. The investigator must fax all serious adverse events (SAEs) identified by the protocol as requiring immediate reporting on an SAE form to the safety desk within 1 working day.

This applies regardless of severity (CTCAE 3.0 grade) and whether or not the SAE is considered related to the use of study drug by the investigator. Where possible, a diagnosis rather than a list of symptoms should be given. The investigator should complete all the details requested including dates of onset, severity, corrective therapies given, outcome and opinion as to whether the adverse event is likely to be drug-related. The investigator should not wait for full details before making the initial report. Personal data have to be replaced by the trial patient number before forwarding any information.

If the event is fatal or life threatening, the investigator must fax any relevant follow-up information of the reported SAE to the safety desk within additional 8 days. If the reported SAE is not fatal or life threatening, the investigator must fax follow-up information as soon as possible.

Via the central safety desk, the National Coordinating Investigator (LKP) will review the SAE again for seriousness and relatedness and assess the SAR for expectedness according to Summary of Product Characteristics Nexavar® Prescribing Information (Fachinformation).

Via the safety desk, the LKP will ensure that the Ethics Committee, competent authority and participating investigators will be informed of all suspected unexpected serious adverse reactions (SUSARs) and all other relevant safety information in accordance with legal requirements.

It is the duty of the safety desk to inform the marketing authorization holder of Sorafenib according to stipulation.

Safety Desk

Studienzentrale SAL

[name]

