#### 6.3.1.6 Laboratory Abnormalities

The following laboratory abnormalities were observed in the phase III advanced RCC (TARGETS) trial:

**Elevated lipase and amylase:** Elevated lipase and amylase levels were very commonly reported. CTC Grade 3 or 4 lipase elevations occurred in 12% of patients in the Sorafenib group compared to 7% of patients in the Placebo group. CTC Grade 3 or 4 amylase elevations were reported in 1% of patients in the Sorafenib group compared to 3% of patients in the Placebo group. Clinical pancreatitis was reported in 2 of 451 Sorafenib treated patients (CTC Grade 4) and 1 of 451 patients (CTC Grade 2) in the Placebo group.

**Hypophosphatemia:** Hypophosphataemia was a common laboratory finding, observed in 45% of Sorafenib treated patients compared to 12% of Placebo patients. CTC Grade 3 hypophosphataemia (1–2 mg/dl) occurred in 13% on Sorafenib treated patients and 3% of patients in the Placebo group. There were no cases of CTC Grade 4 hypophosphataemia (< 1 mg/dl) reported in either Sorafenib or Placebo patients. The etiology of hypophosphataemia associated with Sorafenib is not known.

**Lymphopenia:** CTC Grade 3 or 4 were reported for lymphopenia in 13% of Sorafenib treated patients and 7% of Placebo patients, for neutropenia in 5% of Sorafenib treated patients and 2% of Placebo patients, for anemia in 2% of Sorafenib treated patients and 4% of Placebo patients and for thrombocytopenia in 1% of Sorafenib treated patients and 0% of Placebo.

**Anemia:** Observed in 44% of Sorafenib-treated patients and 49% of Placebo patients. CTCAE Grade 3 or 4 anemia was reported in 2% of Sorafenib-treated patients and 4% of Placebo patients.

**Thrombocytopenia:** Observed in 12% of Sorafenib-treated patients and 5% of Placebo patients. CTCAE Grade 3 or 4 thrombocytopenia was reported in 1% of Sorafenib-treated patients and 0% of Placebo patients.

Further details of the side effect profile of Sorafenib can be found in the current Nexavar® Prescribing Information (Fachinformation).

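### Section 5.1 and Table 14 disagree on blood-pressure frequency after the first 10 drug days, and the rule on laboratory values would under-record silent toxicity if AE pages are the only source

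*Protocol*

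**What the plan says.** **Objective and recording route.** Section 2.3.2 lists as a secondary objective "to compare the toxicity of the Sorafenib and the control treatment". Section 6.2 requires that "All adverse events have to be recorded on the appropriate adverse event pages in the CRF", graded by CTCAE 3.0.

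**Laboratory values.** The AE definition in section 6.1 adds: "The reporting of abnormal laboratory values should be avoided unless they lead to clinical consequences that are not routine". Section 4.1.5.1 presents Table 4 as covering non-hematologic adverse events. Its footnote says that patients with "grade 3 hyperlipasemia or hyperamylasemia without clinical or other evidence of pancreatitis may continue Sorafenib/ Placebo treatment without interruption", at the investigator's discretion. The same footnote covers grade 3 transaminase rises with ALT and AST below 10 times the upper limit of normal. Section 6.3.1.6 gives rates from the renal-cancer trial. Hypophosphatemia was "observed in 45% of Sorafenib treated patients compared to 12% of Placebo patients", and its grade 3 form "occurred in 13% on Sorafenib treated patients and 3% of patients in the Placebo group". Grade 3 or 4 lipase elevation was 12% against 7%. Chemistry including amylase, lipase and phosphate is measured on a fixed schedule in all patients (section 5.1, Tables 14 and 15).

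**Blood pressure.** Under the evaluations during treatment, section 5.1 asks for "Daily measurement of blood pressure during the first three weeks of Sorafenib/ Placebo treatment and weekly for the following three weeks" of study drug. Table 14 in section 5.2 enters "Daily measurement of blood pressure" in the column for days 1 to 22 of the first induction course. It enters weekly readings from day 1 of the second induction course and again through consolidation. Section 4.3.2 gives study drug on days 10 to 19 of each induction course, with the second course starting on day 22 at the earliest.

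**The concern.** On blood pressure, section 5.1 counts from the first dose of study drug, whereas Table 14 counts from the start of chemotherapy. Sites following one text will measure differently from sites following the other. Section 4.1.5.3 says that hypertension on Sorafenib occurs early, so this is a period in which the readings matter.

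On laboratory values, the AE definition filters by clinical consequence, while Table 4 filters by grade. A grade 3 lipase or amylase rise without pancreatitis, with treatment continued, is an adverse event for Table 4. It may have no non-routine consequence, and then section 6.1 steers the site away from reporting it. The protocol does not define what counts as routine, so sites may also differ. At stake is whether a real difference in silent laboratory toxicity between the arms can be seen if the comparison draws on AE pages alone.

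**Working it through.** The plan states no figure on this point to reproduce. The check is a day count and an illustrative power calculation.

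**Blood pressure: day count**

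Inputs: drug on days 10 to 19 of each induction course (19 − 10 + 1 = 10 days per course), and the second course starting at its earliest, day 22. Its drug days are then calendar days 22 + 9 = 31 to 22 + 18 = 40.

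*Days 10 to 19.* Both texts require daily readings, so there is no conflict over the first 10 drug days.

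*Reading A: three calendar weeks from first dose.*
- The window is days 10 to 30, which is 21 days.
- Table 14 is daily through day 21 or 22, depending on whether day 22 belongs to course 1 or course 2. That covers 12 or 13 days.
- The remaining 21 − 13 = 8 or 21 − 12 = 9 days are weekly in Table 14. None is a drug day, since drug resumes on day 31.

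*Reading B: 21 cumulative days on drug.*
- 10 fall in course 1, where Table 14 is daily.
- 21 − 10 = 11 fall where Table 14 is weekly: 10 in course 2 and 1 in the first consolidation course.

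The texts conflict on either reading, but only in the later part of the three weeks.

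**Laboratory values: illustration**

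Inputs: 138 per arm (section 7.1) and renal-cancer rates (section 6.3.1.6). Assumptions: those rates carry over, and a share *f* of abnormalities reaches the AE pages, equal in both arms. The documents give no value for *f*, so a range is shown.

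Formula (two-sided 0.05, normal approximation): power = Φ[(d − 1.96·se0)/se1], where d = f(p1 − p2), se0 uses the pooled proportion and se1 the separate ones.

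For 13% against 3%:
- f = 1: d = 0.10, se0 = √(0.08 × 0.92 × 2/138) = 0.0327, se1 = √[(0.13 × 0.87 + 0.03 × 0.97)/138] = 0.0321. Power = Φ(1.12) = 0.87.
- f = 0.5 (6.5% against 1.5%): d = 0.05, se0 = 0.0236, se1 = 0.0234. Power = Φ(0.16) = 0.56.
- f = 0.25 (3.25% against 0.75%): d = 0.025, se0 = 0.0169, se1 = 0.0168. Power = Φ(−0.48) = 0.32.

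| Reported share *f* | Expected patients, 13% v 3% | Power, 13% v 3% | Power, lipase 12% v 7% |
|---|---|---|---|
| 1 | 17.9 v 4.1 | 0.87 | 0.29 |
| 0.5 | 9.0 v 2.1 | 0.56 | 0.16 |
| 0.25 | 4.5 v 1.0 | 0.32 | 0.10 |

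With an equal share in both arms the ratio 13/3 is unchanged. The absolute difference shrinks in proportion to *f*, and power falls with it.

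**The case against.** **Scheduled laboratory data exist.** Chemistry is measured on schedule in both arms, and nothing keeps the results off the CRF or out of the analysis. Grading of laboratory values may be laid down in the CRF or the SAP. This stands, and it makes the laboratory point conditional. What remains is that the protocol itself fixes the collection rule, spells out only the AE pages as a recording route, and does not say that the scheduled results are entered or graded.

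**Clinical effects are not affected.** A reader might infer that the reporting rules miss what Sorafenib is known to do. The documents do not support that. In Table 18 most of the very common reactions are clinical (hand-foot reaction, rash, diarrhea, hypertension and others) and stay reportable. The section 6.1 sentence also carries an exception for non-routine consequences, so it is not a ban on reporting laboratory values.

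**Hypophosphatemia is not in the Table 4 footnote.** Under Table 4 a drug-related grade 3 case leads to withholding the dose, which may well count as a non-routine consequence. This stands. The 13% against 3% figures therefore show how under-reporting erodes a clear difference; they do not show that these cases go unreported. Lipase fits the footnote more closely, but its rate mixes grades 3 and 4 and power is only 0.29 even with full reporting.

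**The blood-pressure texts may be reconcilable.** Section 5.1 refers to the schedule for details of timing, and footnote a to the tables allows extra readings. But the reference leads to a table that says something different, and the footnote leaves the extra readings to each physician. Neither settles which schedule applies.

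**Conclusion.** Both points hold in limited form.

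The blood-pressure schedules contradict each other after the first 10 drug days: on 8 to 9 non-drug days if calendar weeks are meant, or on 11 of the first 21 drug days if cumulative exposure is meant. The counts assume that course 2 starts on day 22; the cumulative count also assumes that the patient goes on to consolidation with study drug. It would be wrong to infer that the texts conflict over the whole three weeks. No view is taken on which frequency is right.

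The section 6.1 sentence sits badly with Table 4 and with the toxicity objective. If AE pages are the sole source, asymptomatic laboratory toxicity is under-recorded in both arms. Because the trial is double-blind, the expected result is a diluted difference and lost power, not an error favouring one arm's reporting. The fall from 0.87 to 0.56 or 0.32 rests on renal-cancer monotherapy rates carrying over to AML patients on chemotherapy and on an equal reported share. A reader might go further and conclude that most such events would go unreported, but the documents give no figure for that share. The primary EFS analysis is untouched.

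**What to change.** 1. Reconcile the blood-pressure text in section 5.1 with the vital-signs row of Table 14, stating whether the weeks are calendar weeks or days on drug, so that all sites follow one schedule. Cost: wording only.
2. In section 6.1, confine the sentence on laboratory values to what is written on the AE pages.
3. State that the scheduled values of phosphate, lipase, amylase, ALT, AST and bilirubin are graded by CTCAE 3.0 and compared between arms by worst grade per treatment phase, whether or not an AE was reported.

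Items 2 and 3 need no new laboratory tests. They cost some data entry if the results are not already on the CRF, plus grading by program. The downside is that chemotherapy also disturbs these values, so both arms' tables will show more laboratory toxicity.
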